4.4 Treatment Requirements

All eligible patients who consent to this study must have a baseline (post-operative, if surgery is applicable) pre-treatment MRI (please refer to the Imaging Core Manual for more information). This baseline scan must be done within 21 days prior to the initiation of treatment.

Prior to every cycle patients must have:

1) ANC \geq 1500/µl and platelets \geq 100,000/µl.

2) All toxicities recovered to \leq grade 1 (or tolerable grade 2 for non-hematologic toxicity) or \leq baseline.

ABTC # 1801

NCI # ABTC-1801

PI: [name]

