4.5.2 Temozolomide Administration

Temozolomide will be administered orally on an outpatient basis once a day for the number of days indicated by the assigned dose level in 28-day cycles. On the days that pamiparib (BGB-290) is also taken, TMZ should be taken at the same time as the morning dose of pamiparib (BGB-290).

Because Temozolomide is intended for self-administration, if coming to the clinic presents a safety risk, it is permitted to ship the study drug and the appropriate medication diaries to the patient's residence before the scheduled cycle Day 1. The study drug should be shipped by a secure delivery method with package tracking and a delivery confirmation. The regulatory requirements for maintaining investigational product remain and should be addressed and documented.

Phase I Starting Dose: The starting dose of TMZ for the first cohort of patients in the Phase I portion will be a flat dose of 20 mg/day.

Phase II and Surgical Arm (post-surgical treatment cycles): TMZ will be administered at the dose established in the Phase I portion (*dose to be determined*).

Prior to each treatment cycle with temozolomide, a complete blood count (CBC) must be obtained (within -5 days prior to dosing). The start of all TMZ treatment cycles will be scheduled every 4 weeks (28 days, +3 days) after the first daily dose of temozolomide of the preceding treatment cycle.

If liver function tests (alkaline phosphatase, total bilirubin, SGOT, SGPT) are abnormal, the decision to initiate temozolomide treatment should carefully consider the benefits and
ABTC # 1801

NCI # ABTC-1801

PI: [name]

risks for the individual patient. For patients with significant liver function abnormalities, the benefits and risks of continuing treatment should be carefully considered.

Blood counts will be evaluated weekly. Within -5 days prior to first dose of each TMZ treatment cycle, the patient must have an ANC \geq 1500/ul and platelet count \geq 100,000/ul. On Day 1 of each cycle (within -5 days) all **non-hematological** toxicity grades 3 or 4 (except for alopecia, nausea and vomiting), related at least possibly to TMZ must have resolved (NCI Common Terminology Criteria for Adverse Events (CTCAE) grade \leq 1). If toxicity persists, treatment should be delayed by one week for up to 3 consecutive weeks. If after 3 weeks of delay all toxicity has still not resolved then any further treatment with temozolomide should be stopped. See Section 5.2.

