5.0 DOSE MODIFICATION FOR TOXICITY

5.1 Dose Limiting Toxicity (DLT)

A DLT is defined as a clinically significant adverse event or abnormal laboratory value assessed as unrelated to disease progression, intercurrent illness, or concomitant medications and meets any of the criteria below. Any DLT must be a toxicity considered at least possibly related to pamiparib (BGB-290) or TMZ.

ABTC # 1801

NCI # ABTC-1801

PI: [name]

Dose limiting toxicities (treatment related) are defined below. Dose limiting toxicities must have an attribution of possible, probable, or definite to pamiparib (BGB-290) or TMZ. For patients experiencing a DLT, pamiparib (BGB-290) and TMZ will be stopped. If the patient recovers (\leq grade 1 [or tolerable grade 2 for non-hematologic toxicity] or \leq baseline), refer to the Toxicity Management Table below for instruction on whether a dose reduction of TMZ or pamiparib (BGB-290) is required for subsequent doses, or whether pamiparib (BGB-290) and TMZ must be permanently discontinued. Skipped doses will not be made up. If there is any question or confusion concerning a DLT, the treating site should contact the ABTC Central Office to determine patient's DLT status. The ABTC Central Office, with the Study Chair, will make the final decision.

- → Hematological toxicities will be considered dose limiting if any of the following occur and complete blood counts and differentials were obtained according to the mandated schedule (CBC, differential, and platelets drawn twice a week until the ANC ≥ $1500/\mu$ L and platelets ≥100,000/µL): grade 3 or 4 lymphopenia will not be considered a DLT.
 - Grade 4 Neutrophil count decreased (ANC of $< 500/\mu$ L)
 - Grade 4 Platelet count decreased (Platelets $< 25,000/\mu$ L)
 - Grade 3 or 4 Febrile neutropenia
 - Any hematological toxicity that prevents administration of > 80% of the planned TMZ doses for the first cycle

Non-hematological toxicities will be considered dose limiting if any of the following occur:

- Grades 3-4 seizure or intracranial hemorrhage
 - All other grade 3 neurologic toxicity (other than seizure/intracranial hemorrhage) responding *within 3 days* to steroids, anticonvulsants, or electrolyte correction will not be considered dose limiting.
- Grades 3-4 severity with the following exceptions:
 - o except nausea, vomiting, and diarrhea without sufficient prophylaxis *lasting* ≤3 *days*;
 - except alopecia;
 - except grade 3 hyperglycemia;

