Grade 4 Hepatic (> 10 x ULN bilirubin)	Permanently discontinue pamiparib (BGB-290) and TMZ.				
	Note: if grade 3 or 4 hyperbilirubinemia is due to indirect (unconjugated) component only, and hemolysis as the etiology has been ruled out per institutional guidelines, then decrease TMZ by 1 dose level and continue treatment at the discretion of the investigator				
Grade 3 Hepatic (> 5 and ≤ 20 x ULN AST and/or ALT)	Hold pamiparib (BGB-290) and TMZ until AST and/or ALT resolved to $\leq 5 \text{ x ULN}$ or baseline.				
	-if \leq 5 x ULN within 14 days, then decrease pamiparib (BGB-290) and TMZ by 1 dose level				
	-if second episode, permanently discontinue pamiparib (BGB-290) and TMZ				
	-If persistent for > 14 days, permanently discontinue pamiparib (BGB-290) and TMZ				
Grade 4 Hepatic (> 20 x ULN AST and/or ALT)	Permanently discontinue pamiparib (BGB-290) and TMZ.				
Grade 3 Renal (> 3-6 x ULN serum creatinine) and	Permanently discontinue pamiparib (BGB-290) and TMZ.				
Grade 4 Renal (> 6 x ULN serum creatinine)					
Serum creatinine 2-3 x ULN	Hold pamiparib (BGB-290) and TMZ until recovery to grade ≤ 1 or baseline.				
	-if resolved \leq 7 days, then maintain dose levels				
	-if resolved > 7 days, then decrease TMZ by 1 dose level				

ABTC # 1801

NCI # ABTC-1801

PI: [name]

Toxicity	Actions
Hematological toxicity	
Grade 3 Thrombocytopenia (platelets < 50,000 ≥ 25,000/µL)	Hold pamiparib (BGB-290) and TMZ until recovery to platelets \geq 100000 µl or baseline.
	-if resolved \leq 7 days, then maintain dose levels
	-if resolved > 7 days, then decrease TMZ by 1 dose level
Grade 4 Thrombocytopenia (platelets < 25,000/µL)	Hold pamiparib (BGB-290) and TMZ until resolved to platelets ≥ 100000 µl or baseline and decrease TMZ by 1 dose level
Grade 3 Neutropenia (neutrophils < $1,000 \ge 500/\mu$ L)	Hold pamiparib (BGB-290) and TMZ until resolved to $\geq 1500/\mu l$ or baseline
	-if resolved \leq 7 days, then maintain dose levels
	-if resolved > 7 days, then decrease TMZ by 1 dose level
Grade 4 Neutropenia (neutrophils < 500/µL)	Hold pamiparib (BGB-290) and TMZ until resolved to Grade ≤ 1 or baseline and decrease TMZ by 1 dose level
Febrile neutropenia (ANC < 1,000 with single temperature of > 38.3° C or sustained temperature of > 38° C for > 1 hour)	Hold pamiparib (BGB-290) and TMZ until resolved and decrease TMZ by 1 dose level
Grade 2 Anemia (Hb < 10 - 8 g/dL)	First occurrence: continue dosing at current dose level.

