	Second and subsequent occurrences: hold pamiparib (BGB-290) and TMZ until resolved to \leq Grade 1 or baseline:
	-if resolved \leq 14 days, then maintain dose levels
	-if resolved > 14 days, then ↓ TMZ by 1 dose level and continue pamiparib (BGB-290) at same dose
Grade 3 Anemia (Hb < 8 g/dL)	Hold pamiparib (BGB-290) and TMZ until resolved to Grade ≤ 1 or baseline
	-if resolved \leq 7 days, then maintain dose levels
	-if resolved > 7 days, then decrease TMZ by 1 dose level

NCI # ABTC-1801

Toxicity	Actions
Grade 4 Anemia (life threatening consequences; urgent intervention indicated)	Hold pamiparib (BGB-290) and TMZ until resolved to Grade ≤ 1 or baseline and
	decrease TMZ by 1 dose level

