10.1 Off-Treatment Criteria

- 1. Disease Progression: Remove patient from protocol therapy at the time progressive disease is documented. Disease progression is defined as: Progressive neurologic abnormalities not explained by causes unrelated to tumor progression (e.g. anticonvulsant or corticosteroid toxicity, electrolyte abnormalities, hyperglycemia, etc.) or a greater than 25% increase in the measurement of the tumor by MRI scan. If neurologic status deteriorates, on a stable or increasing dose of steroids, or if new lesions appear on serial MRI, further study treatment will be discontinued. Please refer to the Imaging Core Manual for further imaging requirements and submission information.
- 2. Adverse Event:
 - Intercurrent illness that prevents further administration of treatment
 - Patients who experience unacceptable toxicity. Patients removed from study for unacceptable adverse events will be followed until resolution or stabilization of the adverse event.
- 3. Patient Withdrawal: Patient's refusal to continue treatment: in this event, document the reason for withdrawal.
- 4. Non-Compliance: Failure to comply with protocol (as judged by the investigator such as compliance below 80%, failure to maintain appointments, etc.)
- 5. Physician Decision: If at any time the treating physician feels the constraints of this protocol are detrimental to the patient's health remove the patient from protocol therapy.

ABTC # 1801

PI: [name]

- 6. Protocol Defined Delay:
 - Patients will be off treatment who experience a treatment-related toxicity causing a delay in treatment >21 days. Note: Patients who experience grade 3 hepatic toxicity will be off treatment if treatment-is delayed >14 days.
 - Delay in protocol >28 days for major events or other non-treatment related delays
 - Patients who require >2 dose reductions
- 7. Death

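### A first grade 2 anemia worse than baseline at a cycle start is barred from dosing by Section 4.4 but continued by the Section 5.2 toxicity table, and the Day 1 rules elsewhere do not settle which governs

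*Combined protocol and SAP*

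**What the plan says.** **Section 4.4 (Treatment Requirements).** The list opens "Prior to every cycle patients must have" and has two items. Item 1 gives the ANC and platelet thresholds. Item 2 covers all toxicities and requires "grade 1 (or tolerable grade 2 for non-hematologic toxicity", or a level no worse than baseline.

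**Section 5.2 (Toxicity Management Table), grade 2 anemia, hemoglobin below 10 and down to 8 g/dL.** "First occurrence: continue dosing at current dose level". After that: "Second and subsequent occurrences: hold pamiparib (BGB-290) and TMZ until resolved to" grade 1 or lower, or baseline.

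**Sections 4.5.2 and 5.2.1.** Both state a Day 1 rule. In 4.5.2 it begins "Within -5 days prior to first dose of each TMZ treatment cycle, the patient must have an ANC" and goes on to the ANC and platelet thresholds; 5.2.1 is nearly the same. Both also require grade 3 or 4 non-hematologic toxicity to have resolved, with exceptions. Neither sets a hemoglobin or lymphocyte condition, and neither points to item 2 of Section 4.4.

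**Section 5.1.** Under the hematologic dose-limiting toxicities: "grade 3 or 4 lymphopenia will not be considered a DLT". The table in 5.2 has no lymphopenia row.

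**Long delays.** Section 10.1: "Patients will be off treatment who experience a treatment-related toxicity causing a delay in treatment >21 days". The opening paragraph of 5.2.1 instead says that a patient whose treatment-related toxicity is unresolved at 21 days will be considered for pamiparib alone. A later paragraph of 5.2.1 says that after three weeks of delay temozolomide stops and the patient is off treatment.

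**The concern.** Pamiparib is given on all 28 days of each cycle, so a Day 1 that may not start interrupts treatment. A new grade 2 anemia seen at the pre-cycle blood count gets opposite instructions from two operative parts of the protocol, and nothing says which prevails.

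The situation can be expected to arise. Section 9.2.1.2 lists anemia and lymphopenia among the known temozolomide toxicities. Section 9.1.1 requires a blood count with differential within 5 days before each cycle from cycle 2 on, so the triggering value is in hand when the decision is made.

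What is at stake is uniform treatment delivery in a multicenter trial. Two sites with the same patient could act differently and each cite the protocol. Time on treatment then depends partly on which section a site reads, while the primary endpoint is a response confirmed by a second scan at least 4 weeks later (Section 11.0).

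**Working it through.** No sample size, power or error rate is involved, so the check sets the rules side by side.

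**Reach of item 2 in Section 4.4.** It covers all toxicities and is separate from the ANC and platelet item, so it extends to anemia and lymphopenia. The grade 2 allowance is tied to non-hematologic toxicity. A hematologic toxicity therefore blocks the start when it is both above grade 1 and worse than baseline.

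**Cases at a cycle start, with ANC and platelets met:**

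| Case | 4.4 item 2 | 5.2 table | Day 1 rules in 4.5.2 and 5.2.1 |
|---|---|---|---|
| First grade 2 anemia: baseline Hb 12, now 9.5 g/dL | Do not start | Continue at current dose level | No bar named |
| Baseline Hb 9.5, still 9.5 g/dL, first occurrence | Start allowed (at baseline) | Continue | No bar named |
| Second grade 2 anemia, worse than baseline | Do not start | Hold | No bar named |
| Grade 3 or 4 anemia, worse than baseline | Do not start | Hold | No bar named |
| New lymphopenia above grade 1 | Do not start | No row | No bar named |

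**Row 1** is a direct contradiction: one section forbids the dose and the other directs that it continue.

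**Row 2** is not in conflict, and such patients can be enrolled. The eligibility list in Section 3.2 has a floor of 9 g/dL. Its row label is lost in the text available here, and I read it as hemoglobin from the unit. On that reading a patient can enter at 9 to below 10 g/dL, which the table already calls grade 2, and the baseline clause of 4.4 clears that patient.

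**Rows 3 and 4** show 4.4 and the table agreeing, so the table conflict is confined to the first grade 2 occurrence.

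**Row 5** differs in kind. Only 4.4 speaks to lymphopenia at a cycle start, and no section states that such a cycle may begin. The Day 1 rules are silent and do not refer back to 4.4, so sites may read them differently.

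**After 21 days.** If the delay that 4.4 causes exceeds 21 days and the toxicity is treatment-related, Section 10.1 and the later paragraph of 5.2.1 say off treatment. The opening paragraph of 5.2.1 gives consideration of pamiparib alone. The capitalised 21-day rule closing Section 5.1 does not settle this: it covers dose-limiting toxicities, and neither grade 2 anemia nor lymphopenia is listed there in its own right.

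**The case against.** The best defence is that the table governs events during a cycle and Section 4.4 governs Day 1. The protocol is stricter at cycle starts elsewhere: an ANC of 1,000 to 1,500/µL, or platelets of 50,000 to 100,000/µL, has no row in the table, yet Sections 4.4, 4.5.2 and 5.2.1 all block the start. That pattern makes the reading plausible, but it does not settle the anemia case. For those counts the table is silent; for a first grade 2 anemia it gives a positive instruction to continue, without limiting it to mid-cycle.

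The defence is stronger on other points, and these stand:

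- Sections 4.5.2 and 5.2.1 state necessary conditions. Neither says they are sufficient, so they can be applied together with 4.4. A reader might infer that they permit what 4.4 forbids; the wording does not go that far.
- A reader might infer from the dose-limiting exemption and the missing row that no hold for lymphopenia is intended. That does not follow. Grade 3 neutropenia is not itself a listed dose-limiting toxicity, yet the table holds both drugs for it.
- A reader might infer that affected patients are simply removed at 21 days. Section 5.2.1 also names pamiparib alone, and Section 5.2 lets pamiparib continue without temozolomide if approved.
- A reader might want to turn this into a loss of power. The documents give no frequency for the anemia, for delays beyond 21 days or for responses lost, so any such figure would rest on invented inputs.

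**Conclusion.** The contradiction is real and narrow. For a first grade 2 anemia worse than baseline at a cycle start, Section 4.4 and the Section 5.2 table cannot both be followed as written. It does not extend to patients at their baseline grade or to second and later occurrences.

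Two lesser faults go with it. The Day 1 rules in 4.5.2 and 5.2.1 are not tied to item 2 of 4.4, which leaves the handling of new lymphopenia open to local reading. The protocol also gives two outcomes for a treatment-related delay beyond 21 days.

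The size cannot be put in patients or in power. The conclusion rests on reading item 2 as covering hematologic toxicities other than ANC and platelets, which its wording supports, and on the anemia row applying at any time, since it states no limit. The remark about who may enter already at grade 2 also assumes that the 9 g/dL floor is hemoglobin.

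**What to change.** The sponsor should reconcile Section 4.4, Section 4.5.2, the anemia and other hematologic rows of the Section 5.2 table, Section 5.2.1 and Section 10.1 into one start-of-cycle hematologic rule, stated once and cited from each of the others. The text should settle three things:

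1. Whether item 2 of Section 4.4 or the first-occurrence grade 2 anemia row governs on Day 1.
2. Whether lymphopenia counts toward item 2 of Section 4.4.
3. Which outcome applies when a treatment-related delay exceeds 21 days.

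Which rule should stand is a clinical decision for the sponsor, and none is proposed here. The cost is wording, cross-references and a notice to sites. No visits or tests are added, because the pre-cycle blood count with differential is already required.

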4.5 Drug Administration

Phase I portion: To ensure accurate dose level and administration, all participating pharmacies must confirm dose levels with the ABTC Central Office. Please call [contact] to confirm the current dose level before preparing drug for administration.

Treatment will be administered on an outpatient basis. No investigational or commercial agents or therapies other than those described below may be administered with the intent to treat the patient's malignancy.

Patients will be provided with medication diaries (Appendix I) and instructed in their use. Patients will be instructed to bring all unused medication and their diaries to each study visit for assessment of compliance.

4.5.1 Pamiparib (BGB-290) Administration

Pamiparib (BGB-290) capsules should be taken orally with 8 ounces of water. Patients are required to fast for at least one hour before and two hours after each dose of pamiparib (BGB-290). Capsules should be swallowed whole, not chewed or crushed.

Missed doses may be made up if taken within 2 hours after the scheduled administration time. Study drug may not be taken within 8 hours before the scheduled time for administration of the next dose. Patients who vomit after study drug administration should not retake that study drug dose but should resume taking study drug with the next scheduled dose.

Patients should record each dose of pamiparib (BGB-290) on the pamiparib (BGB-290) Patient Medication Diary in Appendix I.

Because Pamiparib (BGB-290) is intended for self-administration, if coming to the clinic presents a safety risk, it is permitted to ship the study drug and the appropriate medication diaries to the patient's residence before the scheduled cycle Day 1. The study drug should be shipped by a secure delivery method with package tracking and a delivery confirmation. The regulatory requirements for maintaining investigational product remain and should be addressed and documented.

Phase I:

Pamiparib (BGB-290) Dose: 60 mg BID

Pamiparib (BGB-290) will be administered twice daily continuously for each 28 day cycle. Each dose should be taken 12 hours apart (± 2 hours), at approximately the same times each day.

ABTC # 1801

NCI # ABTC-1801

PI: [name]

Phase II:

Pamiparib (BGB-290) will be administered twice daily continuously for each 28 day cycle. Each dose should be taken 12 hours apart (± 2 hours), at approximately the same times each day.

Surgical Portion:

Pre-surgery, pamiparib (BGB-290) will be administered twice daily for 6 days prior to scheduled surgery to remove tumor. Each dose should be taken 12 hours apart (± 2 hours), at approximately the same times each day. A final presurgical dose should be taken the morning of surgery, 3-6 hours before the surgical procedure begins.

Post-surgery (upon recovery, within 45 days), pamiparib (BGB-290) will be administered at the dose established in the Phase I portion *(dose to be determined)* twice daily continuously for each 28 day cycle. Each dose should be taken 12 hours apart (\pm 2 hours), at approximately the same times each day.

4.5.2 Temozolomide Administration

Temozolomide will be administered orally on an outpatient basis once a day for the number of days indicated by the assigned dose level in 28-day cycles. On the days that pamiparib (BGB-290) is also taken, TMZ should be taken at the same time as the morning dose of pamiparib (BGB-290).

Because Temozolomide is intended for self-administration, if coming to the clinic presents a safety risk, it is permitted to ship the study drug and the appropriate medication diaries to the patient's residence before the scheduled cycle Day 1. The study drug should be shipped by a secure delivery method with package tracking and a delivery confirmation. The regulatory requirements for maintaining investigational product remain and should be addressed and documented.

Phase I Starting Dose: The starting dose of TMZ for the first cohort of patients in the Phase I portion will be a flat dose of 20 mg/day.

Phase II and Surgical Arm (post-surgical treatment cycles): TMZ will be administered at the dose established in the Phase I portion (*dose to be determined*).

Prior to each treatment cycle with temozolomide, a complete blood count (CBC) must be obtained (within -5 days prior to dosing). The start of all TMZ treatment cycles will be scheduled every 4 weeks (28 days, +3 days) after the first daily dose of temozolomide of the preceding treatment cycle.

If liver function tests (alkaline phosphatase, total bilirubin, SGOT, SGPT) are abnormal, the decision to initiate temozolomide treatment should carefully consider the benefits and
ABTC # 1801

NCI # ABTC-1801

PI: [name]

risks for the individual patient. For patients with significant liver function abnormalities, the benefits and risks of continuing treatment should be carefully considered.

Blood counts will be evaluated weekly. Within -5 days prior to first dose of each TMZ treatment cycle, the patient must have an ANC \geq 1500/ul and platelet count \geq 100,000/ul. On Day 1 of each cycle (within -5 days) all **non-hematological** toxicity grades 3 or 4 (except for alopecia, nausea and vomiting), related at least possibly to TMZ must have resolved (NCI Common Terminology Criteria for Adverse Events (CTCAE) grade \leq 1). If toxicity persists, treatment should be delayed by one week for up to 3 consecutive weeks. If after 3 weeks of delay all toxicity has still not resolved then any further treatment with temozolomide should be stopped. See Section 5.2.

Capsules of temozolomide to be used in this study are available in 20 mg strengths. The dose administered should be recorded in the CRF.

Patients will be instructed to fast during at least one hour before and one hour after administration of temozolomide. Water is allowed during the fast period. Patients should be told to swallow the whole capsules in rapid succession without chewing them. If vomiting occurs during the course of treatment, no re-dosing of the patient is allowed before the next scheduled dose. Missed doses should not be made up. A dose will be considered missed, and should not be made up, if more than 6 hours have passed from the time the dose is normally taken.

Antiemetic prophylaxis with a 5-HT3-antagonist is strongly recommended.

